1. Title

Clinical and Radiographic Outcomes of BIO⁴ Bone Matrix in Patients Undergoing 1 or 2-Level Anterior Cervical Discectomy and Fusion Surgery, CR-16-109, Full Board, Expiration Date 2/21/18

2. Principal Investigator

[name], [name], Department of Surgery and Perioperative Care, Dell Medical School

Co-Investigators:

[name], [name], Department of Surgery and Perioperative Care, Dell Medical School

[name], [name], Seton Spine and Scoliosis Center, Austin TX 78731

Sponsor: Stryker Spine

ClinicalTrials.gov Identifier: NCT03077204

3. Purpose

The goal of this study is to investigate the efficacy of BIO⁴ bone matrix in patients undergoing 1 or 2-level Anterior Cervical Discectomy and Fusion (ACDF) spine surgery. BIO⁴ is a viable bone matrix containing endogenous bone forming cells including mesenchymal stem cells, osteoprogenitor cells and osteoblasts as well as osteoinductive and angiogenic growth factors. BIO⁴ possesses all four characteristics involved in bone repair and regeneration: osteoconductive; osteoinductive; osteogenic and angiogenic (Roberts and Rosenbaum, 2012; Osiris Therapeutics; Bourke et al., 2003). It is an alternative to autograft that minimizes the potential for harvest site co-morbidities (Epstein, 2008, 2009; Eastlack et al., 2014).

Features for BIO⁴ include: next generation viable bone matrix; lot tested for the presence of VEGF (vascular endothelial growth factors) and 70% or greater cell viability post-thaw (Osiris Therapeutics); ready to use out of the package (no decanting required and thaws in 15 minutes); differentiated handling compared to the competition; contains on average at least 600,000 cells (endogenous bone forming cells including mesenchymal stem cells, osteoprogenitor and osteoblasts) per cc (Osiris Therapeutics); and non-immunogenic (Osiris Therapeutics). To date, no other non-cultured cellular bone allografts are promoted as supporting angiogenesis and all four components for bone formation. This study aims to investigate the efficacy of BIO⁴ bone matrix in patients undergoing 1 or 2-level ACDF spine surgery.

Specifically, the study aims to collect the data for ACDF model utilizing BIO⁴ with Bio AVS Cervical Allograft (with graft window). Our null hypothesis is that in ACDF model, the clinical and radiographic outcomes of utilizing BIO⁴ bone matrix with Bio AVS Cervical

Allograft are equivalent to historical high level published data of similar product (Data reported in Meta-analysis ACDF obtained from FDA disc arthroplasty trials).

This White Paper research on new Biologic Platform (BIO⁴ Viable Bone Matrix) will enroll 20 patients. The study with the current sample size tends to serve as an exploratory pathway to another higher Level 1 study with a similar study design. Characteristics of subjects and clinical variables will be analyzed using means and standard deviations calculations. Independent t-tests will be used to compare the means of continuous variables. The normally distributed data will be presented as mean \pm standard deviation. The non-normally distributed data will be expressed as medians (interquartile range) and will be analyzed via the Mann-Whitney's U test. Descriptive variables will be subjected to χ^2 analysis or Fisher's exact test as appropriate. The level of significance will be set at $\alpha=0.05$. SPSS 14.0 for windows statistical software will be used for this study.

4. Procedures

This is a prospective study with the intent to investigate the efficacy of BIO⁴ bone matrix in patients undergoing 1 or 2-level ACDF spine surgery. At the time a patient is scheduled for surgery, the patient's chart will be evaluated for inclusion/exclusion criteria. If a patient meets the criteria for the study, the study will be explained to the patient and consent obtained.

We will utilize the BIO⁴ on label as a 361 HCT/P (human cell, tissue and cellular and tissue-based product) for homologous use for the repair, replacement or reconstruction of bone defects. Interbody fusion (1 or 2-level fusion) in conjunction with an allograft (hct/p) interbody spacer (anterior approach in the cervical spine with hardware) will be utilized. We will also use the Aviator Anterior Cervical Plating System for anterior intervertebral screw fixation of the cervical spine at levels C2-T1. The Aviator Anterior Cervical Plating System is intended for use as an aid in cervical spinal fusion and is intended for unilateral fixation. The Aviator plates are intended to be used with the Aviator bone screws. As a standard of care, there are alternative treatment options for patients who choose not to participate in the study. The patient may still receive ACDF surgery with BIO⁴ bone matrix outside of the study. Additional alternative treatments include continuing conservative care or a different surgical treatment. Conservative care may include: bed rest, back brace, medications for pain, oral steroids, exercise and/or physical therapy, drug injections directly into the spine. The patient may also choose an alternative surgical procedure such as: removing part of the disc (called discectomy) and fusion, and/or removing a small amount of bone from the back of his/her spine (called laminectomy) to possibly help patient's symptoms. Some or all of these alternatives may or may not be appropriate for a given patient. The study doctor can discuss other options with the patient. Only the patient and his/her study doctor can decide if an alternative treatment is appropriate for their condition.

a. Location

Subjects will be recruited from the Seton Spine & Scoliosis Center, Austin, TX. Recruitment will continue until 20 subjects are enrolled and scheduled with 1 or 2-level ACDF spine surgery at levels C2-T1. All the surgeries will take place at Seton Medical Center Austin TX.

b. Resources

Not applicable

c. Study Timeline

The project will take about 12 months from data collection to dissemination of results.

5. Measures

In addition to the basic demographics (age, gender, BMI, smoking status) and operative details (operative time, total blood loss, time of ambulation and perioperative complications), the study aims to collect the data for the following: 1) radiological assessment of fusion (cervical spine x-ray and if needed, CT at 1 year follow up) as the primary endpoint; 2) Arthrodesis rates assessed using CT (1 year follow up, if needed) and AP, lateral, dynamic flexion-extension cervical spine x-rays pre-op, post-op 2~4 weeks (no flexion-extension) (10~34 days post op), 3 months (83~97 days post op), 6 months (173~187 days post op) and 1 year (primary data point outcome) (351~379 days post op); 3) revision rates (if any); 4) outcome scores (Visual Analog Scale, VAS and Neck Disability Index, NDI) pre-op, post-op 2 ~ 4 weeks, 3 months, 6 months and 1 year.

6. Participants

a. Target population

20 individuals who are skeletally mature with cervical pain would be considered as potential subjects for the study.

b. Inclusion Criteria:

- Ages 18 -75 years
- Scheduled 1 or 2-level ACDF spine surgery
- The capacity to provide informed consent.
- Subject has one or more of the following diagnoses:
 - i) Degenerative Disc Disease (as defined by neck pain of discogenic origin with degeneration of the disc confirmed by patient history and radiographic studies)
 - ii) Trauma (including fractures)
 - iii) Tumors
 - iv) Deformities or curvatures (including kyphosis, lordosis, or scoliosis)

- v) Pseudoarthrosis
- vi) Failed previous fusion
- vii) Decompression of the spinal cord following total or partial cervical vertebrectomy
- viii) Spondylolisthesis
- ix) Spinal stenosis

c. Exclusion Criteria

Patients with any of the following conditions will be excluded, or if enrolled and found to be ineligible and do not fit the inclusion criteria, will be withdrawn from the study.

- Patients with current or recent history of malignancy or infectious disease.
- The inability to provide informed consent.
- Subject has marked local inflammation
- Subject has any mental or neuromuscular disorder which would create an unacceptable risk of fixation failure or complications in postoperative care.
- Subject has a bone stock compromised by disease, infection or prior implantation which cannot provide adequate support and/or fixation to the devices.
- Subject has bone abnormalities preventing safe screw fixation.
- Subject has any open wounds.
- Subject has rapid joint disease, bone absorption, osteopenia, osteomalacia, and/or osteoporosis. Osteoporosis or osteopenia are relative contraindications, since this condition may limit the degree of obtainable correction and/or the amount of mechanical fixation.
- Subject has a documented or suspected metal sensitivity.
- Subject is pregnant.
- Subject has anatomical structures or physiological performance that would interfere with implant utilization.
- Subject has inadequate tissue coverage over the operative site.
- Subject has other medical or surgical conditions which would preclude the potential benefit of surgery, such as congenital abnormalities, immunosuppressive disease, elevation of sedimentation rate unexplained by other diseases, elevation of white blood count (WBC), or marked left shift in the WBC differential count.
- Note: The Aviator Anterior Cervical Plating System is not approved or intended for screw attachment to the posterior elements (pedicles) of the cervical, thoracic, or lumbar spine. The surgeon must consider the levels of implantation, patient weight, patient activity level, and other patient conditions which may impact on the performance of the system.

d. Benefits

There are no direct benefits to patients from being in this study. Information gathered in this study may benefit others who undergo this procedure in the future. Long term, studies

like this may help clinicians better understand the benefits of doing spine surgery with BIO⁴ bone graft, BIO AVS cervical allograft and Aviator anterior cervical plating system.

e. Risks

All procedures will be performed by the Board Certificate Orthopedic Surgeons (principal and co-investigators) who have performed several such procedures in the past. The only risks that patients would be subjected to are same that are associated with any such procedures. There may be potential cancer risks associated with similar bone graft products. All the patients will be followed up closely post-operatively for any risks and treated accordingly. There may be confidentiality risks associated with the study. All efforts will be made to minimize this risk.

Subject's participation in this research is voluntary and will be allowed to discontinue from the study anytime he/she wishes to. If the subject choose not to participate, it will not affect his/her relationship with the study doctors or the study doctor's institution, or their right to health care or other services to which they are otherwise entitled at our center. Subject's participation may be stopped by the PI/Co-PI under the following or other circumstances: (1) to protect subject's health and safety, (2) because the subject fails to come in for his/her scheduled study visit, or (3) the study is stopped for any reason.

f. Recruitment

Subjects will be recruited from the Seton Spine & Scoliosis Center, Austin, TX. Recruitment will continue until 20 subjects are enrolled and scheduled with 1 or 2-level ACDF spine surgery at levels C2-T1.

g. Obtaining Informed Consent

The inclusion and exclusion criteria check list will be completed and consent obtained in private in a clinical setting at Seton Spine and Scoliosis Center. After the initial evaluations by investigators, they will address enrollment in the prospective study with his/her patient. Potential subjects will be educated about all essential aspects of the study including the requirements for enrollment, the study procedures, and all risks and benefits of participation. Potential subjects will be given the opportunity to ask questions. After questions have been answered, potential subjects that are interested in enrolling in the study will be asked to sign an informed consent. A copy of the signed informed consent documents will be given to the patient. In the event that a potential subject wishes to deliberate, shows any hesitation, or is not able to decide whether they will participate, the issue of enrollment will be deferred.

7. Privacy and Confidentiality

a. All the required study data will be collected by the study personnel at various study visits. All study personnel are the employed by the clinic and will have access to the patient medical records. During the patient visit, the outcome data such VAS and NDI will be collected on the VAS and NDI forms and scored will be transferred to the data

collection sheet. The forms will be filed in the patient binder. Clinical and demographic data will be captured from the medical record and mentioned in the data collection sheet. These data will be collected at Seton Spine and Scoliosis Center. Specifically, in addition to the basic demographics (age, gender, BMI, smoking status) and operative details (operative time, total blood loss, time of ambulation and perioperative complications), the study aims to collect the data for the following: 1) radiological assessment of fusion (cervical spine x-ray and if needed, CT at 1 year follow up) as the primary endpoint; 2) Arthrodesis rates assessed using CT (1 year follow up, if needed) and AP, lateral, dynamic flexion-extension cervical spine x-rays pre-op, post-op 2~4 weeks (no flexion-extension), 3 months, 6 months and 1 year (primary data point outcome); 3) revision rates (if any); 4) outcome scores (VAS and NDI) pre-op, post-op 2 ~ 4 weeks, 3 months, 6 months and 1 year.

b. The data collection sheet will not have any personal information of subjects (such as date of birth, SSN, etc.). Despite this, all the study documents will be stored locked in a locked office at the Spine Center. The initial data sheet will have a coded number on it, and this coded number will be used to collect follow-up study related information. Only the principal/co-investigators and the study coordinator will have access to the documents. The electronic data sheet will be stored on investigators and study coordinator's Seton computers which are password protected.

c. The study data will be kept for 2 years from the conclusion of the study.

d. Study participants will be assigned a study number, and their data coded and de-identified in the data bases. All efforts will be made to protect the privacy of subjects and maintain confidentiality of data collected. The data collection sheet will not have any personal information of subjects (such as date of birth, SSN, etc.). Despite this, all the study documents will be stored locked in a locked office at the Spine Center. The initial data sheet will have a coded number on it, and this coded number will be used to collect follow-up study related information. Only the principal/co-investigators and the study coordinator will have access to the confidential documents. These confidential documents will not be shared by other researchers for research purposes.

e. At a point after the conclusion of the research study and final analysis, all code and research-related records will be destroyed by study personnel by shredding or other means per discretion of the hospital policy for paper waste containing patient information.

8. Compensation

There will be no remuneration offered for participation in this study.

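### The only hypothesis puts equivalence to historical data in the null, and the listed two-sample difference tests, with no second group, benchmark value, margin or interval, cannot support it

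*Combined protocol and SAP*

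**What the plan says.** The hypothesis is one sentence in Section 3 (Purpose). It opens "Our null hypothesis is that in ACDF model, the clinical and radiographic outcomes of utilizing" BIO⁴ and the Bio AVS Cervical, and ends "Allograft are equivalent to historical high level published data of similar product". No alternative hypothesis follows. The comparator is identified by type of source only: "Data reported in Meta-analysis ACDF obtained from FDA disc arthroplasty trials".

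The same section gives the analysis. "Independent t-tests will be used to compare the means of continuous variables", with Mann-Whitney for non-normal data. "Descriptive variables will be subjected to" chi-square or Fisher's exact test. "The level of significance will be set at" 0.05, with sidedness not stated. Enrolment is 20 patients, and the plan is candid about the purpose of that number: "The study with the current sample size tends to serve as an exploratory pathway" to a higher-level study.

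Section 5 (Measures) names "radiological assessment of fusion (cervical spine x-ray and if needed, CT at 1 year follow up) as the primary endpoint" and makes 1 year the primary time point. VAS and NDI are collected pre-op and at each follow-up visit. No section gives a historical fusion rate, VAS or NDI mean, SD or sample size, and none gives a margin, a confidence interval or a rule for concluding on the hypothesis.

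**The concern.** A significance test can only give evidence against its null. With equivalence in the null, the conclusion favourable to the product (outcomes as good as published ACDF results) is one that the listed tests cannot deliver. If equivalent is loose wording for not different, the null is conventional, but failing to reject it is still not evidence of sameness.

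There is an earlier gap. The t, Mann-Whitney, chi-square and Fisher tests compare two groups, and this study describes one. Rejecting equality would itself need a historical value and sample size that the plan does not supply and that could be chosen after the results are known.

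At stake is the use made of the result. If a non-significant difference in 20 patients were reported as equivalence, it could mislead the planning of the higher-level study that this one is meant to lead to. That planning needs an estimate with its uncertainty, and no interval is planned.

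**Working it through.** **The plan's own figure.** The sample size of 20 cannot be reproduced, because no effect size, rate, SD, margin or power is stated. What can be checked is what 20 patients can show.

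**Inputs from the documents.** n = 20; alpha 0.05; chi-square or Fisher for categorical data; primary endpoint 1-year fusion.

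**Assumptions, because the documents give no values.** Benchmark fusion rate 85-97% in 1-point steps; historical N of 200, 500 or 1000 with an observed rate equal to the benchmark; all 20 evaluable with one fusion result each; two-sided tests. The exact binomial test against a fixed benchmark is not a listed method and is shown for comparison.

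**Step 1. Chance of missing a real deficit.** For true rate p, the miss probability is the sum of C(20,x) p^x (1−p)^(20−x) over all x that give p-value > 0.05.

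Worked case, benchmark 95%: the exact binomial and Fisher tests reject at 16/20 or fewer, so 17 to 20 fusions are non-significant.
- True rate 85% (10 points lower): P(X ≥ 17) = 0.243 + 0.229 + 0.137 + 0.039 = 0.648.
- True rate 75% (20 points lower): P(X ≥ 17) = 0.225.

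Across all assumed benchmarks and historical sizes:

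| Test | Missed, 10 points lower | Missed, 20 points lower |
|---|---|---|
| Exact binomial, minimum-likelihood | 45.5-81.6% | 10.9-45.4% |
| Exact binomial, equal-tailed | 50.8-87.0% | 12.8-53.1% |
| Fisher | 45.5-89.8% | 10.9-60.1% |
| Chi-square, uncorrected | 40.5-81.6% | 9.1-45.4% |

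The overall range for the exact tests at 10 points, 46-90%, is also the range for Fisher alone, which is a listed test.

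**Step 2. One plausible result, 17/20 (85%), against an assumed 95%.**
- Clopper-Pearson 95% CI: lower limit Beta(0.025; 17, 4) = 62.1%, upper limit Beta(0.975; 18, 3) = 96.8%.
- Exact binomial: p = 0.075 (minimum-likelihood) or 0.151 (equal-tailed).
- Fisher: p = 0.102, 0.086 and 0.081 at historical N = 200, 500 and 1000.
- Uncorrected chi-square: p = 0.071, 0.052 and 0.046 at the same sizes. The expected non-fused count is only 1.18, 1.08 and 1.04, so this test is unreliable here.

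With chi-square, the same 17/20 crosses 0.05 or not depending on a historical N that the plan leaves open.

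**Step 3. The best possible result, 20/20.** The lower limit is 0.025^(1/20) = 83.2% (two-sided 95%) or 0.05^(1/20) = 86.1% (one-sided 95%). With an assumed 10-point non-inferiority margin and the benchmark taken as fixed, no result can qualify above a benchmark of about 83.2 + 10 = 93% or 86.1 + 10 = 96% respectively.

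If the true rate equals the benchmark, the chance of meeting that margin is:
- 85% benchmark: at least 19/20 needed, probability 0.176 under both conventions.
- 90% benchmark: 20/20 needed, probability 0.90^20 = 0.122 under both conventions.
- 95% benchmark: zero under the two-sided convention; 20/20 needed, probability 0.95^20 = 0.358, under the one-sided.

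**Step 4. NDI and VAS.** The 95% CI half-width for a mean is t(0.975, 19)/√20 = 2.093/4.472 = 0.47 SD.

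**The case against.** The strongest reply is that this is a small exploratory study that promises no equivalence claim, power or decision rule, and that equivalent in a sentence labelled null hypothesis is probably loose wording for no difference. A reader might infer that the plan will treat p > 0.05 as proof of equivalence. The documents do not support that, because no such rule is written. A reader might equally infer that the plan can at least reject equality. That is also too strong: with no second group, historical value or historical N, equality cannot be tested as written either.

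Three further points have some force. The plan never says that the listed tests will be run on fusion against historical data, so the miss rates illustrate one use of them. Every consequential input is assumed, and the wide ranges largely reflect how few 20 patients are, which the exploratory label already signals. And a reader could derive intervals from a reported fusion count or a mean and SD.

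These points limit the harm but do not remove the defect. The exploratory label explains the sample size; it does not make non-rejection evidence of sameness. The same section still sets a formal null and an alpha, and names no analysis from which equivalence could be concluded. Intervals left for readers to derive do not fix the comparator in advance.

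**Conclusion.** The point holds in limited form and should be fixed. As written, the hypothesis and the listed tests cannot support equivalence on any reading, and even a test of equality needs historical values from outside the plan. Misreading a non-significant result is a risk and not a stated rule.

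Under the assumptions above, a true fusion rate 10 points below the benchmark would go undetected 46-90% of the time with exact binomial or Fisher tests and 40-82% with uncorrected chi-square. A 20-point deficit is missed less often (11-60% and 9-45%). Perfect fusion in all 20 would leave a two-sided 95% lower limit of 83%. The percentages move with the assumed benchmark and historical N; the logical point does not depend on them. The data remain usable, and it is the permitted conclusion that needs correcting.

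**What to change.** In Section 3:

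1. Replace the null-hypothesis sentence with an estimation objective: report the 1-year fusion proportion with an exact (Clopper-Pearson) 95% CI beside the rate from the published source. Fix that source's citation and rate before 1-year data are read.
2. Report NDI and VAS change from pre-op with 95% CIs, using mean change, or median change if the data are clearly non-normal.
3. State that the listed t, Mann-Whitney, chi-square and Fisher tests at 0.05 are exploratory, and that a non-significant difference from historical data will not be reported as equivalence.
4. Only if non-inferiority is to be claimed: put inferiority in the null, pre-specify the margin and confidence level, and require the lower limit to exceed the benchmark minus the margin. Step 3 of the working shows how little 20 patients can support on that route.

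The cost is a few edited sentences and a less favourable permitted conclusion. No extra patients, visits or data are needed.

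### For continuous outcomes the plan names only independent-sample tests: neither suits before-to-after change in VAS and NDI, and Mann-Whitney cannot serve the comparison with published data

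*Combined protocol and SAP*

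**What the plan says.** The whole analysis plan is one paragraph in Section 3 (Purpose) of the combined protocol and SAP. For continuous data it provides:

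- Description: "Characteristics of subjects and clinical variables will be analyzed using means and standard deviations calculations".
- Testing: "Independent t-tests will be used to compare the means of continuous variables".
- Non-normal data: these are to be "expressed as medians (interquartile range) and will be analyzed via" the Mann-Whitney U test.

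The paragraph does not say which groups any test compares. The null hypothesis, also in Section 3, concerns "the clinical and radiographic outcomes of utilizing" BIO⁴ with the cervical allograft, set against historical results described as "Data reported in Meta-analysis ACDF obtained from FDA disc arthroplasty trials". No mean, SD or n from that source is given.

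The study enrols 20 patients in one treated cohort. Section 5 (Measures) lists "outcome scores (Visual Analog Scale, VAS and Neck Disability Index, NDI) pre-op, post-op" at 2 to 4 weeks, 3 months, 6 months and 1 year, and Section 7a repeats this. The scores are therefore taken five times in the same patients. Section 5 also gives "radiological assessment of fusion (cervical spine x-ray and if needed, CT at 1 year follow up) as the primary endpoint". Neither a paired test nor any change-from-baseline or repeated-measures method is named anywhere in the document.

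**The concern.** The named tests fit the data structure only in part. Three comparisons of continuous outcomes are possible.

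- **Cohort against published data.** This is the comparison the hypothesis states. The patients differ, so an independent t-test is the right family. Mann-Whitney ranks individual values and cannot be run from published summaries.
- **Before against after surgery in the same patients.** VAS and NDI are collected in a form that invites this analysis. Both named tests ignore the pairing.
- **Between groups of patients within the cohort.** Both tests would be valid, but the plan defines no such groups.

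An analyst who follows the paragraph literally for before-to-after change would report wrong error bars. An analyst who finds the scores non-normal would be sent to a test that cannot be carried out against the published source. The study is meant to lead to a Level 1 study, for which the SD of within-patient change is a useful planning figure. Per-visit means and SDs alone do not give it to a reader.

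**Working it through.** The plan gives no power, SD, correlation or expected change, so it has no figure to reproduce. What follows illustrates one possible use of the named t-test: pre-op against 1 year in the same patients.

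**Inputs.** From Section 3: n = 20 and α = 0.05. Assumed: a two-sided test (sidedness is not stated), 20 complete pairs, normal scores with equal SD at both visits, and within-patient correlation ρ of 0, 0.3, 0.5 or 0.7.

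**Step 1, standard error of the mean change, in SD units.**
- Independent formula: √(2/n) = √(2/20) = 0.316.
- True value: √(2(1−ρ)/n). At ρ = 0.5: √(1/20) = 0.224.
- Overstatement: 1/√(1−ρ). At ρ = 0.5: 1.41 times.

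**Step 2, 95% half-width, in SD units.**
- Independent: t(0.975, 38) × √(2/20) = 2.024 × 0.316 = 0.640.
- Paired: t(0.975, 19) × √(2(1−ρ)/20). At ρ = 0.5: 2.093 × 0.224 = 0.468.

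**Step 3, true size of the nominal 5% independent t-test.** The sum of the two sample variances is distributed as ((1+ρ)A + (1−ρ)B)/(n−1), where A and B are independent chi-square variables on n−1 df. The mean change is normal with variance 2(1−ρ)/n. Numerical integration of P(|T| > 2.024) gives the sizes in the table. A simulation with 400,000 trials per value of ρ gives 5.00, 2.08, 0.74 and 0.11%.

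Hand check at ρ = 0.5: the effective critical value is 2.024 × 1.414 = 2.863. The Satterthwaite df are 38/(1+ρ²) = 38/1.25 = 30.4. The two-sided tail of t(30.4) beyond 2.863 is 0.75%, in agreement.

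| Assumed ρ | SE overstated | True size | Half-width, independent | Half-width, paired | SD of change / visit SD = √(2(1−ρ)) |
|---|---|---|---|---|---|
| 0 | 1.00 | 5.00% | 0.64 | 0.66 | 1.41 |
| 0.3 | 1.20 | 2.08% | 0.64 | 0.55 | 1.18 |
| 0.5 | 1.41 | 0.745% | 0.64 | 0.47 | 1.00 |
| 0.7 | 1.83 | 0.101% | 0.64 | 0.36 | 0.77 |

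**Step 4, power at ρ = 0.5.** For an assumed true change of 0.5 SD, power is 0.29 with the independent test and 0.57 with the paired test. For 0.8 SD it is 0.76 and 0.92.

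**Step 5, Mann-Whitney.** No arithmetic applies. The statistic needs each patient's value in both groups, and Section 3 refers only to data reported in a meta-analysis.

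**The case against.** The strongest defence is that the test sentence follows the hypothesis closely in the same section, and the hypothesis compares two separate sets of patients. An independent t-test is right for that and can be computed from a published mean, SD and n. This stands. A reader might infer that independent t-tests have no valid use in a one-cohort study; the documents do not support that.

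A reader might also infer that the plan tests before against after with an independent t-test. It does not say so. No objective or hypothesis concerns within-patient change, and a before-to-after test in one cohort would not separate the effect of BIO⁴ from that of the surgery. The table therefore shows what a literal reading could cause and does not measure an error already committed.

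Three further points stand:
- Positive correlation makes the error conservative. False positives are not inflated, and with complete data the estimated mean change is unchanged.
- The loss of power shrinks when the change is large. With an assumed change of 1.2 SD, both tests have power of at least 0.95 at every correlation in the table.
- The team can compute the SD of change from its own coded records (Section 7) until these are destroyed. Only a reader holding per-visit summaries cannot.

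Finally, the plan says "The study with the current sample size tends to serve as an exploratory pathway", and VAS and NDI come last in the list of measures.

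What the defence does not answer is that no named method suits the one comparison over time that the scores allow, and that the stated fallback for non-normal data cannot be applied to the published comparison.

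**Conclusion.** The concern holds in a narrow form, as a minor to should-fix point. The plan names two independent-sample tests for continuous outcomes. The t-test can serve the published comparison, provided that a mean, SD and n are available; Mann-Whitney cannot. Neither suits before-to-after change in VAS and NDI. If the t-test were used there, with 20 complete pairs, equal variances and an assumed ρ of 0.5, its true size would be about 0.7% instead of 5%, and its half-width 0.64 SD instead of 0.47 SD. Over ρ from 0 to 0.7 the size runs from 5.0% down to 0.10%. These values rest on assumed correlations, since the documents give none.

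Per-visit summaries and the primary fusion endpoint are not affected.

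**What to change.** Reword the test paragraph in Section 3:

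1. Analyse VAS and NDI change from pre-op to 1 year within patient, with a paired t-test and 95% CI, or a Wilcoxon signed-rank test if the changes are clearly non-normal. Report the number of complete pairs and the SD of change. The pair count matters because Section 6e foresees missed visits, and a difference of visit means is then no longer the mean within-patient change.
2. Compare continuous outcomes with the published data by a Welch t-test, or a difference with 95% CI, computed from the published mean, SD and n. Do not use Mann-Whitney for this comparison.
3. Otherwise keep independent t-tests and Mann-Whitney only for comparisons between distinct patient groups that the plan defines.

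The cost is wording and slightly more analysis work. No new data, visits or patients are needed. If the correlation were zero, the paired interval would be marginally wider (0.66 against 0.64 SD).
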